5.2 Recruitment Methods

- State how many subjects will be needed.
- Describe when, where, how and by whom potential subjects will be identified and recruited.

[figure not shown]
- Describe materials that will be used to recruit subjects, e.g., advertisements. Include materials as an appendix or separate attachment.
- Describe any payments to subjects, including the amount, timing (at the end of the study or pro-rated for partial study participation), method (e.g., cash, check, gift card), and whether subjects will experience a delay in receiving the payment.

Veteran Participant Recruitment:

All Veteran participants will be current recipients of services at the Houston, New Orleans, or San Antonio VAMCs. Veterans with clinically significant symptoms of anxiety will be included after screening on two occasions to ensure consistency of anxiety symptoms (GAD-7 score of 10 or greater; telephone screen and baseline appointment). Participants will be excluded only for factors that would render bCBT inappropriate for the PCMH setting, including: 1) cognitive impairment, 2) presence of bipolar, psychotic or substance-abuse disorders, 3) Veterans currently receiving psychotherapy for anxiety at the time of enrollment WILL be excluded so as not to duplicate services. For participants who have received a psychotherapy appointment within the last 3 months, we will confirm the treatment provided will not conflict with the study's intervention. The study team will also review information with participating clinicians to confirm they feel the treatments would not conflict with each other. Veterans receiving antidepressant medications at the time of enrollment WILL NOT be excluded.

Based upon sample-size calculations (including attrition over time), the total sample to be randomized is 225. Participants are not randomized until after confirmation of anxiety after the baseline. Because final determination of study inclusion cannot be determined until the baseline appointment, we anticipate needing to provide consent to approximately 425 Veterans total. Approaching Veterans who are not necessarily treatment seeking is a critical component of the project and allows for increased reach to Veterans who might otherwise go unrecognized by the healthcare system. The recruitment procedures comprise four stages designed to maximize reach while minimizing participant burden and confusion about study procedures.

Figure 2. Veteran Recruitment Flow Chart

Stage I:

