Analyses will use data from the mixed-method formative evaluation described above. Qualitative pre-implementation data will be analyzed using rapid qualitative analysis, a systematic and rigorous process, to provide data in real-time to tailor the intervention, and identify contextual barriers prior to rollout^{38,39,40}. Implementation and post-implementation interviews with providers and Veterans will be analyzed using directed content analysis⁴¹ consisting of deductive (a priori) codes from the RE-AIM QuEST framework. Inductive (a posteriori) codes that emerge from providers' and Veterans' experiences with the intervention and VVC-H delivery will also be identified. We will utilize Atlas.ti software to facilitate analysis and management of qualitative data. Quantitative data will be collected and analyzed as descriptive data.

Sample Size and Power Calculations

Primary Aim: To determine whether anxiety symptoms (GAD-7) and quality of life (SF-12) differ as a function of the intervention (bCBT for anxiety vs. EUC) at 4-, 8-, and 12-month follow-ups. A three-step sample-size calculation indicates that 225 anxiety patients will need to be randomized to draw conclusions regarding the primary hypothesis that bCBT will be superior to EUC at 4-, 8, and 12-month assessments.

Step 1: Power to detect GAD-7 differences. A sample size of 138 anxiety patients is needed to detect an effect size = 0.38 for the differences between bCBT and EUC GAD-7 outcomes using a two-sided t-test with 80% power at the .05 significance level, adjusted for repeated measures³⁷. The formula for the sample size, adjusting for repeated measures, is

$$N = \frac{2 * (Z_{(1-\alpha/2)} + Z_{(1-\beta)})^2 [1 + (T - 1) \rho]}{d^2 T}, \text{ where } N \text{ is the sample size per group, } Z_{(1-\alpha/2)} \text{ and}$$

$Z_{(1-\beta)}$ are the $(1-\alpha/2)$ and $(1-\beta)$ percentiles of the normal distribution, T is the number of follow-up measures, ρ is the correlation coefficient of the repeated measurements, and d is the effect size⁴². Solving this with $T = \text{three follow-up measurements after baseline}$, $d = 0.38$, and $\rho = .7$ yields a sample size per group of 69, and total sample $N^t = 138$.

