Quality of Life Outcomes. Our prior study of patients with anxiety or depression¹⁰ resulted in mean, standard deviations, and effect size of 7, 11, and 0.3 respectively for the SF12V mental component score (MCS). SAS[®] proc power indicated that a two-sided t-test with 80% power at the .05 significance level requires a sample of 40 patients per group (80 total). Because the sample required for the anxiety measure (GAD-7; $n=138$) is greater than that needed for the

quality-of-life measure (SF12V; n=80), adjusting for repeated measures, unequal sample, and clustering on provider is presented below for the anxiety measure.

Step 2: Unequal Randomization. To increase power for the project's secondary and implementation outcomes and to reduce unnecessary recruitment, unequal allocation will be used where approximately 60% of Veterans will be randomized to bCBT. As noted by Dumville et al.³⁷, an unequal number of participants per group is an under-used technique that offers advantages for randomized trials, most notably, reduction in unnecessary recruitment. Revised total sample size $N' = N(1+k)^2/4k$, where $N=138$ and $k=1.5$, which gives revised total sample $N'=145$. The individual sample size in each of the two groups are $N'/(1+k)$ and $kN'/(1+k)$; giving $n=58$ in the EUC group and $n=87$ in the bCBT group.

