## DATA ANALYSIS PLAN

### Primary aim: Anxiety and Quality of Life differ as a function of bCBT for anxiety vs. EUC

All analyses will be done on an intention-to-treat basis, and participants will be analyzed in the group to which they were randomized. We will first determine whether participants randomized to the two study arms differed on baseline characteristics, age, race, gender, medical or mental health comorbidities, and anxiety. Chi-square tests will be used for categorical variables and t-test for continuous and ordinal variables.

We will examine the normality of the distributions of both primary outcomes and will consider transformations such as the log or the inverse. Because we are using an unequal randomization (see sample size section), it is especially important to test the assumption about the homogeneity of the variance of the residuals across the levels of the independent variables. For analyses of our primary outcomes, we will test the homogeneity assumption before testing for differences between the bCBT and EUC groups. If the assumption of equal variances is violated, we will use statistical tests such as the approximate t-test, which uses individual sample variances instead of the pooled variance. In addition, we will obtain Satterthwaite's approximation of the degrees of freedom. For the regression models, we will test whether the residual variances are equal and, if necessary, we will fit unequal variance models to obtain better estimates of the standard errors of the difference between groups. We will calculate the absolute differences in outcome measures between baseline and 12-month follow-up and the effect sizes of the bCBT group compared with EUC. We will also examine effect sizes for the bCBT group baseline vs. post-treatment and 8-month follow-up.

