To compare changes in anxiety symptoms between the two groups over time, we will use a longitudinal, mixed-model analysis containing terms for the intercept, treatment, time, and interaction between time and treatment. In separate analyses, we will compare changes in quality-of-life between the two groups over time using a similar mixed-model approach. The mixed-model analysis will allow us to nest patients by site. Any baseline characteristics found to be significantly different between bCBT and EUC will be included in the model, *as will any differences in mental health service use*. The four time points (baseline, 4-, 8-, and 12-month) will allow us to assess the immediate impact of treatment and the longer-term retention, improvement, or decay in outcomes. The treatment effect will measure differences between the intervention and control groups at baseline, and the time effect will measure whether there was an overall change over time in the outcome. The term of most interest will be the interaction between time and treatment, which will indicate whether there is a difference over time between the two groups. The use of the random-coefficient model will allow us to fit a line for each participant using his/her available data, including participants with missing values, and maximize the power to detect differences.

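### The primary mixed model leaves the pre-randomisation baseline free to differ by arm, so its treatment-by-time test compares unadjusted changes and gives up some efficiency, by an amount the documents do not fix

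*SAP*

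**What the plan says.** The SAP (Primary aim) and Protocol 5.6 give the same model for GAD-7 and, separately, for quality of life. It has an intercept, treatment, time and treatment-by-time, with baseline, 4, 8 and 12 months as the outcome visits. On the treatment term both say: "The treatment effect will measure differences between the intervention and control groups at baseline". The interaction is named as the term of main interest. The text then describes a random-coefficient model that fits an individual straight line to each participant.

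Alongside the model, both documents plan a 12-month effect size: "We will calculate the absolute differences in outcome measures between baseline and 12-month follow-up".

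Baseline precedes allocation (Protocol 5.2): "Participants are not randomized until after confirmation of anxiety after the baseline". Entry needs a GAD-7 of 10 or more at both the telephone screen and the baseline appointment (Protocol 5.4).

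Baseline values of the outcome are not a prespecified covariate. Baseline characteristics are tested between arms, anxiety among them, and those that differ significantly are added to the model.

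**The concern.** The true baseline difference between randomised arms is zero in expectation. A model that estimates it freely, and then tests follow-up difference minus baseline difference, carries the sampling error of an unnecessary quantity into the primary test. Using baseline only as far as it predicts follow-up, by a common baseline mean or by ANCOVA, avoids this.

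The conditional covariate rule does not repair it. A covariate that is constant over time shifts every visit equally, so it does not turn the interaction into a baseline-adjusted contrast. If anxiety were added, baseline GAD-7 would be both an outcome row and a covariate.

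What is at stake is power that the trial could have from data it already collects. The plan says it chose this model to maximise power.

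**Working it through.** **The plan's own sample size.** Protocol 5.6 gives a "two-sided t-test with 80% power at the .05 significance level, adjusted for repeated measures", with patients "needed to detect an effect size = 0.38", correlation ρ = .7 and T = "three follow-up measurements after baseline", and says this "yields a sample size per group of 69". The printed formula, two-sided, gives 2(1.960 + 0.842)²[1 + 2(.7)]/(.38² × 3) = 86.97, so 87 per group. With the one-sided value 1.645 it gives 68.5, so 69. The printed 69 is therefore not reproduced two-sided; by the same formula, 69 per group has 70.4% two-sided power. That is a separate matter. The formula averages the follow-ups and does not use baseline, so it does not show what the planned model delivers. Below I take the plan's numbers of patients as given.

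**Inputs.**
- The unequal-allocation step puts 58 "in the EUC group and $n=87$ in the bCBT group".
- After 25% attrition from 145 and 80 randomised: 145 × .75 ≈ 109 bCBT and 80 × .75 = 60 EUC. Dividing by the plan's provider inflation of 1.25, 109/1.25 ≈ 87 effective bCBT.
- Assumed, not in the documents: ρ = .7 also holds between baseline and 12 months, and the baseline and 12-month SDs are equal.

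**12-month contrast, GAD-7, d = .38, 87/60.** In units of the outcome variance:
- Change comparison (as written): 2(1 − ρ) = .60.
- Baseline-adjusted or common baseline: 1 − ρ² = .51, which is 15% smaller.
- 1/87 + 1/60 = .02816.
- As written: .38/√(.60 × .02816) = 2.92, power 83.2%.
- Adjusted: .38/√(.51 × .02816) = 3.17, power 88.7%. Difference 5.5 points.

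At 58/87 the figures are 82.5% and 88.1% (5.6 points). With dropouts' partial data kept (80 EUC and 145/1.25 = 116 effective bCBT randomised; assumed losses of 10%, 8% and 7% before months 4, 8 and 12) they are 85.7% and 89.7%, about 4 points. In simulation (20,000 runs) type I error was 5.1% for both analyses.

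**Sensitivity to the assumptions (87/60).** With s = baseline SD / 12-month SD, the change variance is 1 + s² − 2ρs and the adjusted variance stays 1 − ρ². The excess is (s − ρ)², so it is never negative.

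| ρ | s | As written | Adjusted | Loss (points) |
|---|---|---|---|---|
| .5 | 1.0 | 62.0% | 74.4% | 12.4 |
| .7 | 1.0 | 83.2% | 88.7% | 5.5 |
| .8 | 1.0 | 94.7% | 96.5% | 1.8 |
| .7 | 0.9 | 86.3% | 88.7% | 2.4 |
| .7 | 0.8 | 88.1% | 88.7% | 0.6 |
| .7 | 0.7 | 88.7% | 88.7% | 0.0 |
| .5 | 0.8 | 69.5% | 74.4% | 4.9 |

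**Straight-line model.** This is generalised least squares over four visits at 58/87, with ρ = .7 between all pairs of visits and complete data. If the effect grows linearly to .38 at 12 months, power is 86.2% with free baselines and 91.1% with a common baseline, a loss of 4.9 points. If the effect is .38 from month 4 onward, it is 78.4% and 90.5%, a loss of 12.1. Part of that second gap arises because a straight line misfits a step: the expected 12-month estimate is .342 with free baselines and .376 with a common one.

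**SF-12V.** Protocol 5.6 cites 7, 11 and 0.3 for the mental component and concludes 40 per group. These conflict: 7/11 = .64 needs about 39 to 40 per group, while .3 needs about 174. At 87/60, ρ = .7 and equal SDs, an effect of .3 gives 63.6% against 70.7% (7.0 points); .64 gives 99.8% against 99.96% (about 0.1 point).

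**The case against.** The model as written is standard and valid, and under the base assumptions it has 83.2% power for GAD-7 at 12 months, above the 80% target. Both statements stand. A reader might infer that the primary test is biased or that its error rate is wrong; nothing in the documents or the calculation supports that.

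A reader might also infer a fixed cost of 5 to 7 points across both outcomes. The documents do not support that either. The .7 is stated for the repeated measurements in a formula that counts only follow-ups, and no GAD-7 SDs are given. Equal SDs are doubtful for GAD-7, because the cut-off of 10 is applied at the baseline visit itself and follow-up is unrestricted. The regression of follow-up on baseline has slope ρ/s, so at ρ = .7 and s = .7 the slope is 1 and a change score is already the right adjustment. It is therefore not established that exactly 70% of a chance imbalance should be removed.

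This objection limits the size, not the direction. A cut-off may also lower the correlation, which pushes the loss back up. If it cuts baseline variance to 60% or 40% but leaves the slope at .7, the loss is 3.3 or 2.2 points.

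Finally, a reader might conclude that SF-12V suffers most. That rests wholly on the .3, which the plan's own 40 per group contradicts.

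**Conclusion.** The point holds as one of efficiency. Both documents specify an unadjusted change comparison for both primary outcomes, when a baseline-adjusted one is available from the same data.

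For GAD-7 at 12 months the loss is 5 to 6 power points if ρ = .7 applies between baseline and 12 months with equal SDs, and about 4 if partial data are used. Over the inputs examined it runs from about 0 to 12 points. Under the straight-line model it is 4.9 or 12.1 points, depending on whether the effect builds up or is present from month 4; in the second case the model as written falls just below 80%. For SF-12V the loss is about 7 points or about 0.1, depending on which of the plan's two effect sizes is meant.

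The change is worth making because the direction is certain for the 12-month contrast and the remedy needs no new data. It does not call the validity of the trial into question.

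**What to change.** In the SAP (Primary aim) and Protocol 5.6:
- Fit the same mixed model with one baseline mean common to both arms, for GAD-7 and SF-12V: keep baseline as an outcome row, drop the treatment main effect and keep the treatment-by-time terms.
- State whether time is categorical or linear. A separate 12-month contrast needs categorical time.
- In place of the raw baseline-to-12-month difference, report the baseline-adjusted 12-month difference between arms in scale points with its confidence interval. If it is also standardised, name the SD and note that the GAD-7 baseline SD is restricted by the entry cut-off. At an SD ratio of .8, dividing by the baseline SD gives an effect size 1/.8 = 1.25 times that from the 12-month SD.
- Do not add the baseline value of the modelled outcome as a covariate while it is also an outcome row. For GAD-7 this concerns the anxiety item on the tested list; SF-12V is not named there.

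The cost is a few sentences in two documents and one fewer parameter per model. The equal-baseline assumption is secured by randomisation, including under the cut-off, which is applied before allocation. The change should be fixed before outcome data are seen by arm.

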The project will embed bCBT into PCMHI programs using existing VHA providers. A total of 225 Veterans diagnosed with an anxiety disorder will be recruited from three VAMCs. Eligible Veteran participants will be randomized to a bCBT or to an Enhanced Usual Care (EUC) condition. A professionally diverse set of PCMHI providers will be invited to deliver bCBT. Providers will receive bCBT training and support to embed treatment into their existing practice setting. Veterans randomized to bCBT will receive 4 – 9 sessions based upon treatment response (50% reduction in GAD-7) by session 4. Veterans will also be offered the choice of receiving bCBT in-person or through VVC-H. EUC participants will receive 4 brief monthly check-in calls from study staff and a note placed in their medical record alerting their provider to the presence of significant anxiety symptoms. BCBT treatment and EUC check-in calls will end at 4 months.

The project leverages VA stakeholders at all levels to improve alignment of the work with VA and Veteran initiatives. Clinical outcomes will provide justifications or cautions to inform future evidence-based psychotherapy (EBP) programs. If positive, data will be used to assist VA leadership in the expansion of EBPs and VVC-H in PCMHI. For example, should the project produce robust clinical outcomes - next steps would involve a non-research / demonstration project in one or two VISNs where the project team will train and support a wider group of providers in the delivery of brief CBT for anxiety. The project team will use the training program and clinical intervention materials as well as lessons learned from the proposed HSR&D IIR to support and enhance brief CBT delivery in a non-research context.

List of Abbreviations

Provide a list of all abbreviations used in the protocol and their associated meanings.

ACOS – Associate Chief of Staff
AUDIT-C – Alcohol Use Disorders Identification Test
bCBT – Brief Cognitive Behavioral Therapy
CAPRI – Compensation and Pension Record Interchange
CBT – Cognitive Behavioral Therapy
CCI – Charlson Comorbidity Index
CoE – Center of Excellence
Co I – Co-Investigator
CPRS – Computerized Patient Record System
DSM-5 – Diagnostic and Statistical Manual of Mental Disorders version 5
DSMB – Data Safety Monitoring Board
EBP – Evidence Based Practice
ERS – Expectancy Rating Scale
EUC – Enhanced Usual Care
FE – Formative Evaluation
GAD – Generalized Anxiety Disorder
GAD-7 – General Anxiety Disorder (7-item scale)

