3.0 Objectives

- Describe the study's purpose, specific aims, or objectives.
- State the hypotheses to be tested.
- Indicate the relevance to Veterans and the VA

The primary hypothesis is that anxiety outcomes, as measured by the GAD-7, and quality of life, measured by the SF-12 will be superior at 4-, 8-, and 12-month follow up for patients who are assigned to receive bCBT vs. EUC.

Primary Aim: To determine whether anxiety symptoms (GAD-7) and quality of life (SF-12) differ as a function of the intervention (bCBT for anxiety vs. EUC) at 4-, 8-, and 12-month follow-ups.

Secondary Aims: (Prediction of bCBT response and VVC-H use (bCBT group only)): A) To identify factors associated with bCBT response, namely whether bCBT is effective for specific anxiety disorders (e.g. generalized anxiety, panic, social phobia) and whether number of sessions received, and treatment engagement are critical to outcomes. B) To identify Veteran demographic and clinical factors associated with VVC-H use.

Exploratory Aims: A mixed-methods formative evaluation, informed by RE-AIM QuEST, will collect data related to Reach (#of Veterans receiving bCBT and VVC-H), Effectiveness (bCBT and VVC-H impact), Adoption (# of providers using bCBT and VVC-H), and Implementation (provider bCBT program fidelity and VVC-H potential). Data will be collected from qualitative interviews with Veterans and providers and integrated with quantitative data from provider surveys and chart reviews of bCBT and VVC-H use. With the ORD supplement to the main project, [name] will leverage the diverse Veteran populations included in the multisite

parent study (Houston, San Antonio, and New Orleans VA MCs) to understand barriers to treatment and research access for African American and Hispanic Veterans.

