During active treatment, clinicians will be asked to discuss anxiety symptoms and response with participants as part of the treatment process. Providers will be encouraged to deliver bCBT as long as it remains appropriate for any given patient. If a patient is discovered to have additional needs that make the use of bCBT inappropriate, the clinician can opt to seek additional or alternative care for the patient. The presence of severe depression, substance abuse, and comorbid PTSD could all require the clinician to change or add treatments. At the end of the 4-month treatment period, clinicians will be encouraged but not required to discontinue treatment. For patients who reach the response criterion, clinicians will introduce the potential for treatment discontinuation. For patients who do not reach the targeted anxiety goal by the final session (4th session), clinicians will work with the patient to determine whether additional sessions would be helpful. The provider will have the option to continue care or refer the patient to other therapies that are not a part of the research study based on their clinical judgment.

Figure 1. Response to bCBT and Determination of Treatment Ending

The proposed bCBT intervention (See Appendix 5G) uses a patient-centered approach to increase engagement while addressing the mental health needs of anxious Veterans. A bCBT provider manual and a patient workbook provide structure and increase Veteran participation. The patient workbook will be made available both in hard copy and in an electronic version. The workbook includes intervention session information and worksheets, along with homework assignments to engage Veterans during VVC-H sessions and facilitate between-session activities. The bCBT intervention skill modules use CBT-based techniques established in our prior trials^{10, 11} and flexibly apply these skills to improve anxiety symptoms and overall quality of life (see Table 1). All participants take part in an initial session where they receive psychoeducation on anxiety and the bCBT treatment approach, set goals, and begin self-monitoring. Three core skill sessions focused on relaxation, cognitive, and exposure techniques follow. Participants who do not show treatment response at session 4 will be offered up to 4 additional cognitive and/or exposure skill sessions. All participants receive a final wrap-up session to review gains and plan for maintenance of skills.

Table 1. bCBT Intervention Overview

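### As most naturally read, the key test compares linear slopes over 0–12 months, which matches neither the hypothesis at 4, 8 and 12 months nor the quantity the trial was sized on

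*SAP*

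**What the plan says.** The primary-aim section of the SAP and protocol section 5.6 give the same model in essentially the same words.

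- **Model terms.** It is a "mixed-model analysis containing terms for the intercept, treatment, time, and interaction between time and treatment".
- **Key term.** "The term of most interest will be the interaction between time and treatment".
- **Form of time.** "The use of the random-coefficient model will allow us to fit a line for each participant using his/her available data". No categorical time, change point or visit contrast is named.
- **Treatment main effect.** "The treatment effect will measure differences between the intervention and control groups at baseline". Any benefit must therefore show in the interaction.
- **Purpose of the visits.** "The four time points (baseline, 4-, 8-, and 12-month) will allow us to assess the immediate impact of treatment", and then whether the outcome is retained, improves further or decays.
- **Effect sizes.** The plan gives baseline to 12-month differences and effect sizes against EUC. For post-treatment and month 8 it mentions effect sizes for the bCBT group.

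Protocol section 3.0 states the hypothesis that anxiety and quality of life "will be superior at 4-, 8-, and 12-month follow up for patients who are assigned to receive bCBT vs. EUC". Step 1 of the sample-size part of section 5.6 uses a repeated-measures formula with three follow-ups, correlation .7 and effect size 0.38.

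On timing, the protocol abstract says "BCBT treatment and EUC check-in calls will end at 4 months". Section 5.1 says that at the end of that period "clinicians will be encouraged but not required to discontinue treatment".

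**The concern.** A single slope per arm represents a benefit that builds at a constant rate for a year. If most of the benefit arrives during the treatment period and then holds or fades, a straight line describes it poorly. A fade pulls the slope difference towards zero even while bCBT is better at every follow-up. One line per arm also cannot separate the immediate effect from later retention, improvement or decay, which is what the plan says the four visits are for.

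There are three quantities in play: superiority at each of three visits (the hypothesis), a difference averaged over three visits (the sample size), and a difference in slopes (the key test). They can give different answers from the same data. If the choice among them is left until the data are seen, the primary result is open to selection. If the slope is kept as the key test, a real but early benefit could be reported as no effect.

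**Working it through.** **1. The quantity the trial was sized on.** Step 1 of the protocol's calculation is N per group = 2(z₁₋α/₂ + z₁₋β)²[1 + (T−1)ρ] / (d²T), with T = 3, ρ = .7, d = 0.38. The factor [1 + 2(.7)]/3 = 0.8 is the variance of the mean of three follow-up scores with SD 1, so the formula powers an arm difference averaged over the follow-ups.

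With two-sided .05 and 80% power it gives 2(1.960 + 0.842)²(2.4)/(0.1444 × 3) = 86.97, or 87 per group. The protocol states 69, which corresponds to a one-sided .05 (68.5). That is a separate matter and is not used below.

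**2. Effective sample.** I accept the protocol's own allowances: 145 bCBT × 0.75 / 1.25 = 87, and 80 EUC × 0.75 = 60. The multiplier is √[1/(1/87 + 1/60)] = 5.959.

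**3. Slope test.** Visits are at 0, 4, 8 and 12 months. Centred times are −6, −2, 2, 6, with sum of squares 80. For arm differences (0, δ₄, δ₈, δ₁₂) in SD units, the slope difference is (−2δ₄ + 2δ₈ + 6δ₁₂)/80. With equal correlation ρ, its per-patient variance is (1 − ρ)/80, which is 0.00375 (SD 0.0612) at ρ = .7. Then z = slope/0.0612 × 5.959, with a two-sided .05 test.

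**4. Baseline-adjusted follow-up average.** Its variance is 0.8 − r², where r is the correlation of each follow-up with baseline. For an average effect of 0.38:

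- r = .7: z = 0.38/√0.31 × 5.959 = 4.07, power 98%.
- r = .4: z = 0.38/√0.64 × 5.959 = 2.83, power 81%.

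**5. Results.** The average follow-up effect is 0.38 in every row. The trajectories are assumptions.

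| Difference at 4/8/12 months | Slope per month | z, ρ = .7 | Slope-test power | Adjusted average, r = .7 |
|---|---|---|---|---|
| 0.38/0.38/0.38 | 0.0285 | 2.77 | 79% | 98% |
| 0.50/0.38/0.26 | 0.0165 | 1.61 | 36% | 98% |
| 0.57/0.38/0.19 | 0.0095 | 0.92 | 15% | 98% |
| 0.19/0.38/0.57 | 0.0475 | 4.62 | above 99% | 98% |

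**6. Sensitivity.**

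- At ρ = .5 throughout, the slope variance is 0.5/80 = 0.00625. The first three rows fall to 57%, 24% and 11%.
- With a random-slope SD of 0.03 per month at ρ = .7, the variance is 0.00375 + 0.0009 = 0.00465 and the constant case falls from 79% to 70%.
- With baseline correlation .4 and follow-up correlation .7, the slope variance is (80 − 5.6 − 28.8)/6400 = 0.007125. The slope test then has 52% for the constant case and 92% for the growing case, against 81% for the adjusted average in both.

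**7. Fit of the line.** For a constant 0.38, the intercept difference is 0.285 − 6 × 0.0285 = 0.114. The fitted differences at months 0, 4, 8 and 12 are 0.11, 0.23, 0.34 and 0.46, against true values of 0, 0.38, 0.38 and 0.38.

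**The case against.** **Linear time is inferred.** The documents never say that time is continuous. Categorical fixed time with random patient coefficients is possible, and the aim of showing immediate impact and later change fits visit-level time. This stands as a limit on certainty. It does not remove the point, because under that reading too no contrast at 4, 8 or 12 months and no multiplicity rule is given.

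**There may be another between-arm test.** The same section mentions an approximate t-test with Satterthwaite degrees of freedom, separately from the regression models, and the sample size refers to a t-test. The visits for that test are not stated, so it adds ambiguity but does not supply the missing contrasts. Likewise, the phrase on effect sizes against EUC could be read as covering all visits. The most that can be said is that between-arm estimates at months 4 and 8 are not clearly planned.

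**The slope test is not always weak.** For a constant effect at correlation .7 its 79% is close to the design's 80%. For steady growth it is at least as powerful as the average. This stands in full.

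**Month 4 is not a firm end of treatment.** Section 5.1 qualifies the abstract, and section 5.1 also lets EUC patients receive psychotherapy. A step by month 4 is plausible but not documented. The argument needs only a trajectory that may not be straight.

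**Visit differences need not be read off the lines.** A reader might infer from step 7 that the reported visit effects will be biased. The plan names no such output and calculates the 12-month change separately. The fitted values show only that the line describes a constant benefit badly.

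**The free baseline difference is not an error.** Estimating it does not bias a correctly specified model; constraining it is a matter of efficiency.

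**Conclusion.** The point holds on the natural reading of the text: the key term is a linear slope difference, and it matches neither the hypothesis nor the follow-up average behind the sample size. The cost depends on the trajectory. With an average effect of 0.38, slope-test power runs from 15% (the stronger assumed fade) through 79% (constant) to above 99% (steady growth). The adjusted average stays at about 98%, or 81% if the baseline correlation is .4. These figures assume SD 1, equal correlation of .7, and effective groups of 87 and 60.

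A reader might conclude that the trial will probably miss a real benefit. The documents do not support that: they give no expected trajectory, and they name decay only as one of three possibilities. What is established is a mismatch in the primary analysis that could turn an early or fading benefit into a null result, together with no clear between-arm comparison at two of the three visits in the hypothesis.

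**What to change.** In the SAP and protocol section 5.6:

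1. Model time as a categorical factor with arm and arm-by-time terms and an unstructured covariance. Adjust for the baseline score, or keep baseline as a response with the arm means constrained equal.
2. Name one primary contrast in advance. The arm difference averaged over the three follow-ups would match the sample-size formula.
3. Report between-arm differences with confidence intervals at 4, 8 and 12 months. An averaged contrast alone does not show superiority at each visit, so state a multiplicity rule if that is to be claimed.
4. Keep the linear-slope model as descriptive.

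The cost is wording and a few more covariance parameters, which 225 patients can support; no new data are needed. The trade-off is somewhat less power than the slope test if the benefit grows steadily and the baseline correlation is low (81% against 92% at a baseline correlation of .4).
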